### **10.3. Patient withdrawal**

Not applicable

### **10.4. Institutional review board (IRB)/Independent ethics committee (IEC)**

There must be prospective approval of the study protocol, protocol amendments, and other relevant documents (e.g., informed consent forms if applicable) from the relevant IRBs/IECs. All correspondence with the IRB/IEC must be retained. Copies of IRB/IEC approvals must be forwarded to Pfizer.

## **11. MANAGEMENT AND REPORTING OF ADVERSE EVENTS/ADVERSE REACTIONS**

This study involves data that exist as structured data by the time of study start. In these data sources, individual patient data are not retrieved or validated, and it is not possible to link (ie, identify a potential association between) a particular product and medical event for any individual. Thus, the

PFIZER CONFIDENTIAL

minimum criteria for reporting an AE (ie, identifiable patient, identifiable reporter, a suspect product, and event) cannot be met.

[figure not shown]

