**9.2. Setting**

The secondary data collection will be exclusively from the Indonesia Vaccine Safety Website as requested by BPOM (Indonesia National Regulatory Authority). After the study protocol is approved by BPOM (Indonesia National Regulatory Authority), structured data will be obtained retrospectively for all AEs reported following administration of the BNT162b2 mRNA vaccine, starting from the time of vaccine available in Indonesia. Structured anonymized data for events which includes the following information will be collected and used for analysis:

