**B4. Solicited AEs:**

PFIZER CONFIDENTIAL

B4.1.. Local reactions : pain, swelling, redness, thickness.

B4.2. Systemic reactions: fever, myalgia, malaise

B5. Unsolicited AEs:

B5.1. Local reactions: abscess, bleeding, etc.

B5.2. Systemic reactions: headache, nausea, arthralgia, etc.

Events for which either of the above is missing will not be recorded for analysis.

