### **9.3. Variables**

Variable	Role	Data source(s)	Operational definition
The type of vaccination with BNT162b2 mRNA vaccine following which SAE was reported	Baseline characteristics	Indonesia Vaccine Safety Website	Whether the AE was reported after primary series or booster vaccination
Onset of SAE	Baseline characteristic	Indonesia Vaccine Safety Website	Whether the serious AE onset $\leq$ 30 mins or $>$ 30 mins
Causality	Baseline characteristics	Indonesia Vaccine Safety Website	Whether the SAE was caused by the vaccine. Causality of the AE with BNT162b2 – classified as WHO criteria as coincidence, ISRR, vaccine reaction, unclassifiable, or indeterminate)
Type of AE	Baseline characteristics	Indonesia Vaccine Safety Website	Whether the AE was Serious and Non-serious or solicited and unsolicited

PFIZER CONFIDENTIAL

Type of solicited reaction	Baseline characteristics	Indonesia Vaccine Safety Website	Whether the AE was local or systemic
Type of Solicited Local reaction	Baseline characteristics	Indonesia Vaccine Safety Website	Whether the AE was pain, swelling, redness or thickness
Type of Solicited Systemic reaction	Baseline characteristics	Indonesia Vaccine Safety Website	Whether the AE was fever, myalgia, malaise
Type of unsolicited reaction	Baseline characteristics	Indonesia Vaccine Safety Website	Whether the AE was local or systemic and the term reported
Type of unsolicited local reaction	Baseline characteristics	Indonesia Vaccine Safety Website	Whether the AE was abscess, bleeding, etc.
Type of unsolicited systemic reaction	Baseline characteristics	Indonesia Vaccine Safety Website	Whether the AE was headache, nausea, athralgia, fatigue, etc
Seriousness	Baseline characteristics	Indonesia Vaccine Safety Website	Whether the AE was serious according to Indonesia MoH decree (require hospitalization, life-threatening, cause persistent or significant disability/ incapacity, or suspected to cause death) or non-serious

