#### 9.5. Study size

This is a descriptive study without a statistical hypothesis and hence sample size calculation is not applicable. In this study all the AEs reported following administration of BNT162b2 mRNA vaccine

will be collected retrospectively from the onset of this vaccine administration in Indonesia till the time of approval of this study.

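### Does Section 11's statement that product and event cannot be linked undermine the reporting position or the causality outcome?

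*Combined protocol and SAP*

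**What the plan says.** Section 11 makes two statements about the data. The first is that "individual patient data are not retrieved or validated". The second is that "it is not possible to link (ie, identify a potential association between) a particular product and medical event for any individual". From these it concludes that the "minimum criteria for reporting an AE (ie, identifiable patient, identifiable reporter, a suspect product, and event) cannot be met".

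Section 9 describes the same data differently. Under Section 9.2, "structured data will be obtained retrospectively for all AEs reported following administration of the BNT162b2 mRNA vaccine". Later in that section, completeness is judged event by event: "Events for which either of the above is missing will not be recorded for analysis". Section 9.3 defines the causality variable as "Whether the SAE was caused by the vaccine", with the categories "classified as WHO criteria as coincidence, ISRR, vaccine reaction, unclassifiable, or indeterminate". The same table records whether the event followed the primary series or a booster, and whether a serious event began within 30 minutes or later. Causality of serious events is secondary outcome B2.

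Sections 9.1 and 10.1 state that the data are anonymized and that no recipient identification is collected.

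**The concern.** Section 11 sets a low bar for a link: a potential association is enough. Yet every record enters the dataset because someone reported that event after that vaccine. Onset in minutes has meaning only if a vaccination and an event are tied together in one person. Read literally, Section 11 would leave outcomes A1, A2, B1 and B2 impossible to derive. If Section 9 is right instead, part of the stated reason for not reporting cases is false.

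This is a safety study requested by the national regulator. If the reporting position rests on a wrong description of the data, serious events already judged to be vaccine reactions might sit with the sponsor and be passed to no one. It might also be doubted whether B2 can be produced at all.

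**Working it through.** There is no figure to reproduce. Section 9.5 says: "This is a descriptive study without a statistical hypothesis and hence sample size calculation is not applicable". The check is one of consistency, in four steps.

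1. **Is the link sentence compatible with the data definition?** No. Section 9.2 restricts the data to reports after one named vaccine, and Section 9.3 adds a causality class for serious events. A potential association between product and event is therefore present in each record.

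2. **Does Section 11's conclusion fall with the sentence?** Its four criteria are joined by *and*, so the set fails if any one fails. Taking them in turn:
   - Suspect product: met by design (Section 9.2).
   - Event: met by design (Sections 9.1 to 9.3).
   - Identifiable patient: plausibly unmet. Section 9.1 collects no recipient identification, and Section 10.1 says that the data hold no personal information.
   - Identifiable reporter: plausibly unmet. No reporter field appears among the variables in Section 9.3, and Section 9.6 ties the extract to those variables.

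   Two of the four are met and two are plausibly not. One failure is enough, so the conclusion stands on grounds found elsewhere in the protocol.

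3. **Is outcome B2 in doubt?** B2 is a frequency by category. Section 9.3 gives the source of the category as the vaccine safety website, so the study team does not have to judge any case. B2 could be tabulated from de-identified event records, or from counts supplied by the database owner. The completeness rule in Section 9.2 could be applied at extraction, and the age summaries in Section 9.7 could be supplied ready-made. Neither proves that individual patient data must reach the sponsor, and neither is blocked if they do not.

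4. **Would safety information be left without a route?** Section 12 requires the sponsor to be told immediately of new information that could bear on the product's benefit-risk assessment. The reports also come from the national database and are analysed at the regulator's request (Section 7), so they are already inside national surveillance. The causality breakdown of serious events is itself a planned result.

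**The case for a change.** The strongest case for a change is that Section 11 never cites anonymization. It argues from the missing link straight to the criteria, so a reader cannot tell whether the position was reached on the true facts. Quality control is given as not applicable (Section 9.8), and Section 9.9 rules out data validation, so no later step would catch the mismatch. The Section 12 clause is general, sits under dissemination, and sets no specific step for serious events classed as vaccine reactions. Rewording is cheap, and an anonymized listing of such events could be drawn from planned variables.

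Much of this is fair. The sentence is wrong for this data source, and the protocol would read better if Section 11 named the criteria that are unmet and why. It is also true that Section 12 is not a case-level procedure.

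What does not stand is the step from a wrong sentence to a wrong action. The criteria can fail on patient and reporter alone. A listing for matching against cases that the sponsor already holds answers no requirement in the documents. Matching is doubtful as well, because the variables in Section 9.3 include no identifiers, dates or reporter. The listing would add little to B2, which already reports the causality classes.

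**Conclusion.** The inconsistency is real but is a drafting slip. Correcting it would alter no outcome, no estimate and no reporting action that the documents show to be required. Two of Section 11's four criteria are met by design, contrary to its wording. The other two are plausibly unmet, and either one suffices for its conclusion. Outcome B2 can be produced as planned. Analysts will take the causality class from the source database whatever Section 11 says.

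This rests on two assumptions. First, the extract contains what Section 9.3 lists and no reporter field. Second, an identifiable patient is read in its plain sense. The protocol does not define the term, and Section 9.7 does mention age and gender; under a looser reading, the reporter criterion alone would still carry the conclusion. The number of serious events classed as vaccine reactions is not given in the documents, so no count of affected cases can be stated. No change to the plan follows.

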## **12. PLANS FOR DISSEMINATING AND COMMUNICATING STUDY RESULTS**

In the event of any prohibition or restriction imposed (eg, clinical hold) by an applicable competent authority in any area of the world, or if the investigator is aware of any new information which might influence the evaluation of the benefits and risks of a Pfizer product, Pfizer should be informed immediately.

#### **14. LIST OF TABLES**

None

#### **15. LIST OF FIGURES**

None

PFIZER CONFIDENTIAL
